8.4.3.1. Exposure During Pregnancy

For both unapproved/unlicensed products and for marketed products, an exposure during pregnancy (EDP) occurs if:

- A female becomes, or is found to be, pregnant either while receiving or having been exposed (e.g., because of treatment or environmental exposure) to the investigational product; or the female becomes or is found to be pregnant after discontinuing and/or being exposed to the investigational product;
 - An example of environmental exposure would be a case involving direct contact with a Pfizer product in a pregnant woman (eg, a nurse reports that she is pregnant and has been exposed to chemotherapeutic products).

- A male has been exposed (e.g., because of treatment or environmental exposure) to the investigational product prior to or around the time of conception and/or is exposed during his partner's pregnancy.

If a patient or patient's partner becomes or is found to be pregnant during the patient's treatment with the investigational product, the investigator must submit this information to Pfizer Safety on the CT SAE Report Form and EDP supplemental form, regardless of whether an SAE has occurred. In addition, the investigator must submit information regarding environmental exposure to a Pfizer product in a pregnant woman (e.g., a patient reports that she is pregnant and has been exposed to a cytotoxic product by inhalation or spillage) to Pfizer Safety using the EDP supplemental form. This must be done irrespective of whether an AE has occurred and within 24 hours of awareness of the exposure. The information submitted should include the anticipated date of delivery (see below for information related to termination of pregnancy).

Follow-up is conducted to obtain general information on the pregnancy and its outcome for all EDP reports with an unknown outcome. The investigator will follow the pregnancy until completion (or until pregnancy termination) and notify Pfizer Safety of the outcome as a follow up to the initial EDP supplemental form. In the case of a live birth, the structural integrity of the neonate can be assessed at the time of birth. In the event of a termination, the reason(s) for termination should be specified and, if clinically possible, the structural integrity of the terminated fetus should be assessed by gross visual inspection (unless pre-procedure test findings are conclusive for a congenital anomaly and the findings are reported).

If the outcome of the pregnancy meets the criteria for an SAE (i.e., ectopic pregnancy, spontaneous abortion, intrauterine fetal demise, neonatal death, or congenital anomaly [in a live born baby, a terminated fetus, an intrauterine fetal demise, or a neonatal death]), the investigator should follow the procedures for reporting SAEs.

Additional information about pregnancy outcomes that are reported to Pfizer Safety as SAEs follows:

- Spontaneous abortion includes miscarriage and missed abortion;
- Neonatal deaths that occur within 1 month of birth should be reported, without regard to causality, as SAEs. In addition, infant deaths after 1 month should be reported as SAEs when the investigator assesses the infant death as related or possibly related to exposure to the investigational product.

Additional information regarding the EDP may be requested by the sponsor. Further follow-up of birth outcomes will be handled on a case-by-case basis (e.g., follow-up on preterm infants to identify developmental delays). In the case of paternal exposure, the investigator will provide the patient with the Pregnant Partner Release of Information Form to deliver to his partner. The Investigator must document in the source document that the patient was given Pregnant Partner Release of Information Form to provide to his partner.

8.4.3.2. Exposure During Breastfeeding

Scenarios of exposure during breastfeeding must be reported, irrespective of the presence of an associated SAE, to Pfizer Safety within 24 hours of the investigator's awareness, using the CT SAE Report Form. An exposure during breastfeeding report is not created when a Pfizer drug specifically approved for use in breastfeeding women (eg, vitamins) is administered in accord with authorized use. However, if the infant experiences an SAE associated with such a drug's administration, the SAE is reported together with the exposure during breastfeeding.

8.4.3.3. Occupational Exposure

An occupational exposure occurs when during the performance of job duties, a person (whether a healthcare professional or otherwise) gets in unplanned direct contact with the product, which may or may not lead to the occurrence of an adverse event.

An occupational exposure is reported to Pfizer Safety within 24 hours of the investigator's awareness, using the CT SAE Report Form, regardless of whether there is an associated SAE. Since the information does not pertain to a patient enrolled in the study, the information is not reported on a CRF; however, a copy of the completed CT SAE Report Form is maintained in the investigator site file.

8.4.4. Medication Errors

Other exposures to the investigational product under study may occur in clinical trial settings, such as medication errors.

Safety Event	Recorded on the CRF	Reported on the CT SAE Report Form to Pfizer Safety Within 24 Hours of Awareness
Medication errors	All (regardless of whether associated with an AE)	Only if associated with an SAE

8.4.4.1. Medication errors

Medication errors may result from the administration or consumption of the investigational product by the wrong patient, or at the wrong time, or at the wrong dosage strength.

Medication errors include:

- Medication errors involving patient exposure to the investigational product;
- Potential medication errors or uses outside of what is foreseen in the protocol that do or do not involve the participating patient.

Such medication errors occurring to a study participant are to be captured on the medication error page of the CRF, which is a specific version of the AE page.

In the event of a medication dosing error, the sponsor should be notified immediately.

Whether or not the medication error is accompanied by an AE, as determined by the investigator, the medication error is recorded on the medication error page of the CRF and, if applicable, any associated AE(s), serious and non-serious, are recorded on an AE page of the CRF.

Medication errors should be reported to Pfizer Safety within 24 hours on a CT SAE Report Form **only when associated with an SAE**.

8.4.4.2. Lack of Efficacy

Lack of efficacy is reportable to Pfizer Safety only if associated with an SAE.

9. DATA ANALYSIS/STATISTICAL METHODS

Detailed methodology for summary and statistical analyses of the data collected in this study will be documented in a Statistical Analysis Plan, which will be maintained by the Sponsor. This document may modify the plans outlined in the protocol; however, any major modifications of the primary endpoint definition and/or its analysis will also be reflected in a protocol amendment.

9.1. Sample Size Determination

This study does not include any formal sample size determination. Approximately 150 patients with Ph+ CML will be enrolled including at least 45 CP, AP, and BP patients in the 4th or later line treatment setting. With a subset of 45 patients, the standard deviation of an estimate of the probability of response is at most 0.075.

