monitoring of BCR-ABL transcript levels and mutational analysis of the BCR-ABL kinase domain will be performed by a central laboratory and carried out by independent central analysis. Patient participation will conclude not more than 4 years after the first dose.

Study Treatment

Patients will receive bosutinib 500 mg orally once daily with food. Bosutinib commercial formulation of 100 mg and 500 mg tablets will be provided.

Statistical Methods

This study does not include any formal sample size determination. Approximately 150 patients with Ph+ CML will be enrolled including approximately 45 CP, AP, and BP patients in the 4th or later line treatment setting.

The primary analyses will be the percentage of cumulative confirmed MCyR (for CP Ph+ CML patients) and cumulative confirmed OHR (for AP and BP Ph+ CML patients) by 1 year of bosutinib treatment (week 52). Confirmed MCyR will be defined as (1) the attainment of confirmed MCyR (CCyR or PCyR) by 1 year for patients entering the study without CCyR achieved on the previous TKI therapy or (2) the maintenance of confirmed CCyR (achieved under the previous TKI therapy) for at least 1 year after starting treatment with bosutinib or (3) at least MMR by 1 year and a deeper molecular response compared to baseline. Patients with baseline PCyR that do not achieve CCyR are included in the analysis but they would be counted as non-responders. Initial cytogenetic (in the absence of MMR) and hematologic responses must be confirmed by 2 consecutive assessments at least 28 days apart.

Secondary efficacy analyses include the percentage of cumulative MCyR, cumulative confirmed OHR, cumulative MMR, cumulative best response, landmark MCyR and OHR, cumulative confirmed CHR, duration of CCyR and duration of MMR.

All treated Ph+ CML patients with a valid baseline efficacy assessment for the respective endpoint will be included in the molecular, cytogenetic, and hematologic efficacy analyses. All treated Ph+ CML patients will be included in the other efficacy analyses. Analyses will be presented by disease stage (e.g., CP, AP, BP) and/or line of therapy (e.g., CP 2nd line [CP2L], CP 3rd line [CP3L], CP 4th or later line [CP4L], AP2L, AP3L, AP4L, BP2L, BP3L, BP4L).

Ph- CML patients will be analyzed separately and only for cumulative CHR and molecular endpoints.

Descriptive summaries and confidence intervals (if applicable) will be provided; no inferential analyses are planned for this study.

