2. STUDY OBJECTIVES AND ENDPOINTS

Primary Objective(s):	Primary Endpoint(s):
To estimate the 1-year (52-week) probability of cumulative confirmed Major Cytogenetic Response (MCyR) in CP Ph+ CML patients with 1 or 2 prior lines of TKI therapy.	Cumulative confirmed MCyR defined as Complete Cytogenetic Response (CCyR) or Partial Cytogenetic Response (PCyR) by 1 year (52 weeks) in 2nd and 3rd line CP patients.
To estimate the 1-year (52-week) probability of cumulative confirmed MCyR in CP Ph+ CML patients with 3 or more prior lines of TKI therapy.	Cumulative confirmed MCyR by 1 year (52 weeks) in 4th and later line CP patients.
To estimate the 1-year (52-week) probability of cumulative confirmed Overall Hematological Response (OHR) in AP and BP Ph+ CML patients with any prior TKI therapy.	Cumulative confirmed OHR defined as Complete Hematological Response (CHR) or Return to Chronic Phase (RCP) by 1 year (52 weeks) in AP and BP patients.
Secondary Objective(s):	Secondary Endpoint(s):
Efficacy	
To estimate the cumulative probability of MCyR in each disease phase (CP, AP and BP) for Ph+ CML patients.	Cumulative MCyR in CP, AP and BP patients.
To estimate the cumulative probability of confirmed OHR in each disease phase (AP and BP) for Ph+ CML patients by number of lines of prior therapy.	Cumulative confirmed OHR in AP and BP patients by line of therapy.
To characterize the distributions of best response (molecular, cytogenetic, or hematologic) in the CP, AP, and BP Ph+ CML patient populations.	Cumulative best response in CP, AP, and BP patients.
To estimate the probability of MCyR at 3, 6, 12, 18, and 24 months in the CP, AP, and BP Ph+ CML patient populations.	MCyR at 3, 6, 12, 18, and 24 months in CP, AP, and BP patients.
To estimate the probability of confirmed OHR at 3, 6, 9, 12, 18, and 24 months in the AP and BP Ph+ CML patient populations.	Confirmed OHR at 3, 6, 9, 12, 18, and 24 months in AP and BP patients.
To estimate the probability of cumulative confirmed CHR in the CP, AP and BP Ph+ CML patient populations.	Cumulative confirmed CHR.
To estimate the probability of cumulative major molecular response (MMR) in the CP, AP, and BP Ph+ CML patient populations.	Cumulative MMR in CP, AP, and BP patients.
To estimate the duration of CCyR.	Duration of CCyR.
To estimate the duration of MMR.	Duration of MMR.

Safety	

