6.1. Screening

Screening can be accomplished over one or multiple visits over a 4-week period (30 days). Stage of disease is defined as the worst phase of CML experienced by the patient, regardless of disease status at the time of study entry. For example, a patient whose disease is in CP at study entry, but who had been previously diagnosed in AP, will be classified as AP CML. Refer to [Appendix 7](#) for specific criteria for CP, AP and BP phases of disease.

Prior cancer history, including CML and any other cancer will be collected. All treatments received by the patient for CML (CP, AP, and BP), including dates of administration, dose(s), best response and tolerability (including specific intolerance(s) to each therapy) will be collected from the time of original diagnosis of CML. Any additionally diagnosed malignancies will also be recorded at screening.

All relevant medical history and treatment received by the patient within 30 days before administration of bosutinib will be recorded on the patient's CRF, including the name of the procedure or drug and other related information.

The following procedures should be conducted as part of the baseline screening:

- Signature of informed consent document (ICD);
- Review of patient's eligibility (i.e., protocol inclusion/exclusion criteria);
- Cytogenetic confirmation of Ph+ chromosome (or BCR-ABL1+ if Ph-) CML diagnosis and phase. Acceptable documentation includes results from primary CML diagnosis or results following discontinuation/ failure of prior CML therapy. Either traditional cytogenetics for the Ph+ chromosome or fluorescence in situ hybridization (FISH) for the BCR-ABL juxtaposition or PCR for BCR-ABL transcript quantification are acceptable for the diagnosis of CML;
- Medical history;

- Complete physical examination to include vital signs (sitting or supine blood pressure, heart rate, and height and weight);
- Smoking status at screening; (Note: the use of TKIs could lead to cumulative long-term cardiovascular disease therefore information of other risk cardiovascular factors like smoking status will be collected for this study);
- Extramedullary disease assessment (including assessment of liver, spleen and lymph nodes by physical examination as well as other potential sites of extramedullary involvement);
- ECOG performance status ([Appendix 8](#));
- Electrocardiogram (ECG);

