5.4. Other Analysis Sets

The evaluable analysis set are those treated patients with a valid baseline efficacy assessment for the respective endpoint (ie, [1] at least 20 metaphases from the baseline bone marrow cytogenetic assessment or a CCyR with at least 200 cells analyzed from the fluorescence in situ hybridization [FISH] baseline assessment or MMR from the baseline molecular assessment for cytogenetic endpoints or [2] a valid baseline hematologic assessment for hematologic endpoints as defined in [Appendix 1](#) or [3] a valid baseline molecular assessment from the central laboratory for molecular endpoints).

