5.5. Treatment Misallocations

B1871039 is a single arm study so there will be no treatment misallocations. Patients who are enrolled but not treated will not be included in the safety or efficacy analyses.

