8.2.1. Analysis of Primary Efficacy Endpoints

The response rate analyses are based on the evaluable analysis set for Ph+ CML patients only. The primary efficacy analysis is the percentage of responders by Week 52, done separately for:

- Confirmed MCyR for combined CP2L and CP3L;
- Confirmed MCyR for CP4L;
- Confirmed OHR separately for AP and BP.

Any patient not demonstrating a response by Week 52 is deemed a non-responder.

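### Is the 0.075 precision figure in Protocol 9.1 a problem, given that its 45 patients are not the fourth-line primary analysis set?

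*Protocol*

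**What the plan says.** Protocol 9.1 opens by stating that there is no formal sample size determination. It then plans about 150 Ph+ patients, "including at least 45 CP, AP, and BP patients in the 4th or later line treatment setting", and adds: "With a subset of 45 patients, the standard deviation of an estimate of the probability of response is at most 0.075".

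The fourth-line primary endpoint in Protocol 2 is narrower: "Cumulative confirmed MCyR by 1 year (52 weeks) in 4th and later line CP patients". SAP 8.2.1 lists the matching analysis as "Confirmed MCyR for CP4L" and runs it on the evaluable set. SAP 5.4 defines that set: "The evaluable analysis set are those treated patients with a valid baseline efficacy assessment for the respective endpoint". The first sentence of Protocol 9.2.1 leaves out CP for the fourth line, but the sentence after it confines MCyR to CP patients.

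Three rules govern who moves from the 45 into CP4L:

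- Phase (Protocol 6.1): "Stage of disease is defined as the worst phase of CML experienced by the patient". A patient in CP at entry with earlier AP therefore counts as AP.
- Treatment (SAP 5.5): "Patients who are enrolled but not treated will not be included in the safety or efficacy analyses".
- Baseline validity, as in SAP 5.4.

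The Statistical Methods part of the Protocol Summary words the number slightly differently: "including approximately 45 CP, AP, and BP patients in the 4th or later line treatment setting".

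**The concern.** The study only estimates. SAP 4 has no hypotheses and no decision rules, so precision is the only quantitative basis for its size, and 0.075 is the only precision figure in either document. It sits directly after a minimum that pools CP, AP and BP, yet no primary endpoint is estimated in that pooled fourth-line group. A reader could attach 0.075 to the fourth-line primary result, when the analysed set may be smaller and its interval wider. If so, the reduction of the fourth-line target from 75 to 45 would look better supported than it is for the endpoint that matters. What is at stake is how a planning statement is read. No estimate would be biased.

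**Working it through.** **Reproducing the plan's figure.** The SD of an estimated proportion is sqrt(p(1−p)/n), largest at p = 0.5. With n = 45 from Protocol 9.1, sqrt(0.25/45) = 0.0745. This satisfies the stated bound of 0.075.

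**Number needed for the bound.** 0.25/0.075² = 44.4, so 45 patients. At 44 the worst case is 0.0754, which still rounds to 0.075; at 43 it is 0.076. A set of exactly 45 has almost no margin.

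**Can the 45 shrink before analysis?** There are three routes.

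1. *No valid baseline.* Inclusion criterion 1 (Protocol 4.1) requires screening marrow cytogenetics with at least 20 metaphases unless MMR is shown by qRT-PCR. SAP 5.4 accepts at least 20 metaphases, a CCyR by FISH with at least 200 cells, or baseline MMR. An eligible CP patient is therefore normally evaluable, apart from deviations.
2. *Enrolled but untreated.* Registration comes after eligibility is confirmed and within 3 days before the first dose (Protocol Table 1 footnote i, and 6.2). Little loss is expected.
3. *AP or BP by worst phase.* This route is open. The documents give no split of fourth-line patients by phase, so its size is unknown.

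In the other direction, 9.1 sets a floor, so fourth-line enrolment may exceed 45.

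**How much would a shortfall matter?** The sizes below 45 are assumptions. The interval is the exact (Clopper-Pearson) 95% CI named in SAP 8.1.3, taken near 50% response.

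| Evaluable CP4L | Maximum SD | Responders | Exact 95% CI | Half-width |
|---|---|---|---|---|
| 45 | 0.0745 | 22 | 0.337 to 0.642 | 15 points |
| 40 (assumed) | 0.0791 | 20 | 0.338 to 0.662 | 16 points |
| 35 (assumed) | 0.0845 | 17 | 0.314 to 0.660 | 17 points |
| 30 (assumed) | 0.0913 | 15 | 0.313 to 0.687 | 19 points |

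**When the bound survives a smaller n.** Setting sqrt(p(1−p)/n) = 0.075 gives p = (1 − sqrt(1 − 4n × 0.075²))/2.

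- n = 40: 4 × 40 × 0.005625 = 0.900, so p = 0.342.
- n = 35: 4 × 35 × 0.005625 = 0.7875, so p = 0.270.
- n = 30: 4 × 30 × 0.005625 = 0.675, so p = 0.215.

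The bound still holds when the response rate is at or below these values, or at or above their mirror values (0.658, 0.730, 0.785).

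**What depends on 0.075.** Nothing in the SAP takes it as an input. Response rates are reported with exact intervals on the evaluable number. SAP 8.2.2 also records that every patient had reached Week 52 before 11 March 2020, so rewording 9.1 could no longer affect recruitment.

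**The case for a change.** The strongest case for acting is that an estimation study should state its precision for the sets it estimates in. Protocol 1.2.3 defends the smaller fourth-line cohort by saying numbers in each cohort are sufficient, but those cohorts are lines of therapy with phases pooled, not the primary analysis sets. The sentence before the 0.075 ties it to the pooled group. No CP4L minimum appears anywhere, and neither CP2L with CP3L, nor AP, nor BP has any precision statement. A clarifying line would cost nothing.

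Much of this stands. The population mismatch is real, and the bound is not secured for CP4L. What does not stand is the step from there to a defect. The sentence is true of any 45 patients and does not name MCyR, CP4L or a primary endpoint. The documents contain no figure showing that evaluable CP4L is below 45. The adequacy that Protocol 1.2.3 records, after CHMP feedback, is for an informative descriptive analysis, which does not rest on a particular SD. Precision for AP and BP could not be filled in from the documents either, since no expected numbers by phase are given.

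The variations in the stated number are clerical. The Summary's background text says at least 45, as 9.1 does, so the single approximate wording in its Statistical Methods is a stray word. Protocol 1.2.3 and SAP 2 still open with 75, but the next paragraph in each explains the move to 45.

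**Conclusion.** No change is needed. The figure is right for 45 patients, and it carries over to the fourth-line primary estimate only if evaluable CP4L reaches about that number or the response rate is far enough from 50%. The plan does not guarantee either condition, and the documents do not show that either fails. The one substantial route of loss is the unknown AP and BP share.

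Even if that share brought CP4L down to an assumed 30 to 40, the worst-case SD would be 0.091 to 0.079 and the interval half-width near 50% response would be 1 to 4 points wider than at 45. The exact interval reported with the result will show this directly. Extra precision figures in 9.1 would describe the planning more fully but would alter no estimate, interval or decision. An analyst or reader can obtain the CP4L worst case from sqrt(0.25/n) once the evaluable number is known.

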9.2. Efficacy Analysis

All treated Ph+ CML patients with a valid baseline efficacy assessment for the respective endpoint (Evaluable Population) will be included in the molecular, cytogenetic, and hematologic efficacy analyses. All treated Ph+ CML patients (Full Analysis Set [FAS]) will be included in the other efficacy endpoints. Analyses will be presented by disease stage (e.g., CP, AP, BP) and/or line of therapy (e.g., CP 2nd line [CP2L], CP 3rd line [CP3L], CP 4th or later line [CP4L], AP2L, AP3L, AP4L, BP2L, BP3L, BP4L) for Ph+ CML patients. All Ph- CML patients will be analyzed separately and only for cumulative CHR and molecular endpoints.

Descriptive summaries and confidence intervals (if applicable) will be provided; no inferential analyses are planned for this study.

9.2.1. Analysis of Primary Endpoint

The primary efficacy analyses are the percentage of cumulative confirmed MCyR in CP 2nd and 3rd line patients, cumulative confirmed MCyR in 4th and later line patients and the cumulative confirmed OHR in AP and BP patients by 1 year of bosutinib treatment (Week 52) assessed from the local laboratory data. The primary analyses will be the percentage of cumulative confirmed MCyR (for CP Ph+ CML patients) and cumulative confirmed OHR

(for AP and BP Ph+ CML patients) by 1 year of bosutinib treatment (week 52). Confirmed MCyR will be defined as (1) the attainment of confirmed MCyR (CCyR or PCyR) by 1 year for patients entering the study without CCyR achieved on the previous TKI therapy or (2) the maintenance of confirmed CCyR (achieved under the previous TKI therapy) for at least 1 year after starting treatment with bosutinib or (3) at least MMR by 1 year and a deeper molecular response compared to baseline. Patients with baseline PCyR that do not achieve CCyR are included in the analysis but they would be counted as non-responders. Initial cytogenetic (in the absence of MMR) and hematologic responses must be confirmed by 2 consecutive assessments at least 28 days apart.

